Groups to be recruited will include:

Both patients and healthy, non-patient, normals

Which if any of the following vulnerable populations will be recruited as subjects?

Children, Employees or lab personnel

Vulnerable populations require special protections. How will you obtain informed consent, protect subject confidentiality, and prevent undue coercion?

Parents will provide informed consent for participation of their children in the study. This would prevent undue coercion of this vulnerable population. Subject confidentiality would be maintained by coding of all specimens. Family participation would be entirely voluntary.

To protect employees' participating in interviews, the study team will ensure confidentiality by anonymizing responses and storing data securely. Participation will be voluntary, with verbal consent obtained (see section S). Interviews will take place in a private setting.

E3. Pregnant woman/fetus

Will pregnant women and/or fetuses (as described in 45 CFR 46 Subpart B) be enrolled in the research?

No

E4. Neonates

Will neonates of uncertain viability or nonviable neonates (as described in 45 CFR 46 Subpart B) be enrolled in the research?

No

E5. Children

Will children be enrolled in the research?

Yes

Section F: Design/Procedure

F1. Design

Select one category that most adequately describes your research:

e) Specimen/laboratory experiment

Discuss the research design including but not limited to such issues as: probability of group assignment, potential for subject to be randomized to placebo group, use of control subjects, etc.

We propose to recruit 40 newborns every year from various NICUs in Texas for WGS, RNAseq, and metabolomics. The primary outcome will be effectiveness of Consultagene, defined as difference in diagnostic yield compared to usual care. Secondary outcomes will include 1) change in clinical care attributable to genomic results measured by adapting the harmonized measure from the Clinical Sequencing Evidence-Generating Research (CSER) consortium; and 2) caregivers' experience with and perceptions of genomic sequencing and Consultagene assessed with validated measures of caregiver outcomes. Data will be collected via Consultagene, surveys, and qualitative interviews.

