A stepped wedge cluster-randomized trial design will be used to implement the program and to evaluate the effectiveness of Consultagene (primary outcome) in providing genomic care to newborn infants in the RGV and El Paso. The Consultagene platform will be implemented in nine under-resourced NICUs, matched into cohorts based on size (number of beds), and rural/urban status. Based on those characteristics, we will have cohort triads (three NICUs each) which will be simultaneously randomized to the time at which the intervention is implemented.

Inclusion Criteria:

Inclusion criteria: Undiagnosed infants from 0-90 days of age, with a diverse group of phenotypes and strongly suspected to have genetic disorders will be recruited. Samples from biological parents will be obtained whenever available.

Clinicians will be included for interviews who use the Consultagene portal for the MAGNET study.

Exclusion Criteria:

Exclusion criteria include: (1) abnormal noninvasive prenatal testing (NIPT) suggesting chromosomal abnormality; (2) abnormal amniocentesis results, (3) abnormal newborn screening indicating an inborn error of metabolism; (4) abnormal FISH results for aneuploidy (trisomy 18, 13, or monosomy X); (5) Down syndrome; (6) dysmorphic features in the absence of other congenital anomalies; (7) isolated birth defects such as myelomeningocele, cleft lip/palate, cardiac septal defects, isolated congenital diaphragmatic hernia, etc.; (8) birth defects due to known teratogens i.e., alcohol, Isotretinoin, etc.; (9) multiple congenital anomalies associated with maternal diabetes; (10) VACTERL association; and (11) hemodynamically unstable newborns needing transport for higher level of care.

F2. Procedure

We will execute broad reliance agreements and contracts with the NICUs participating in the study after IRB approval. Baylor IRB will serve as the IRB of record for all participating sites. SMART IRB agreement will be used as the basis for reliance. An amendment will be submitted to add each participating site after the reliance agreements are established and before work commences at each site. BCM staff will conduct the research on sites.

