Based on the established inclusion and exclusion criteria, when a neonate seen by our NICU partners at level III/IV units is ascertained to need genetics consultation, the provider (neonatologist or nurse practitioner) will inform the BCM research coordinator and establish care for that patient through Consultagene portal as a peer-to-peer consultation journey. This study is based on peer to peer referral which means that patients will not be able to sign up themselves in the study. Providers will enter individuals' data into Consultagene after informed consent is obtained. Consent will be obtained by BCM research personnel and, where included in individual hospital contracts, by research coordinators at participating institutions. The research team will only obtain consent after reliance agreements have been established with different institutions.

Families accepted in the study will be contacted by the study team at BCM for video education on research study, virtual evaluation of the neonate and multi-omic study, including WGS, RNAseq, and metabolomics study. Board-certified medical geneticists and counselors at BCM will perform remote genetic evaluations using iPads at the bedside, with assistance from the local provider/research coordinator. Additional evaluations will cover various systems, and photographs will be taken with parental permission.

Research photographs taken for clinical assessment will be securely managed to protect participant privacy and confidentiality. The images will be stored on encrypted devices or secure servers, accessible only to authorized research personnel. The purpose of these photographs is to document physical features relevant to the study, enabling researchers to make accurate clinical assessments during virtual evaluations. Any identifiable information will be removed or obscured when sharing images in reports or presentations, ensuring that the photographs are used strictly for research and clinical evaluation purposes. Families will opt in for specific use of photos as per the informed consent form. The photos will not be destroyed unless the subject withdraws from the study.

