How many subjects (or specimens, or charts) will be used in this study?

Local: 410 Worldwide: 410

Please indicate why you chose the sample size proposed:

Primary Outcome Power Calculation: One of the relevant indicators of the clinical impact is percentage of babies who need genetic screening getting diagnosis. Based on the current published estimates, we anticipate that about 10% of babies at NICU will need genetic screening, and 60% of those babies will likely need to be evaluated by genomics. Currently, none of the 9 participating clinics have performed any WGS or RNA sequencing (baseline). We estimate that about 1/10 of babies who need screening get genetic diagnoses based on the use of other diagnostic methods such as karyotype and chromosomal microarray analysis available to the neonatologists. After the program of genetic screening or Consultagene platform is established and implemented, we expect that all babies who need genetic screening (10/10) or need further genomics evaluation (~6/10) (60%) will receive it. And about 50% of those getting genomics evaluation will get a diagnosis, i.e., 30% of babies who need genetic screening will get a diagnosis.

We do not have prior data on intra-class correlation for NICUs, but we expect it to be large. Specifically, we use different sizes of the cluster (4, 5, 6) i.e. number of babies per NICU requiring genetic screening from whom data will be collected in each time step. Additionally, difference of the correlation values are employed (0.5, 0.6, 0.7). As the intervention effect is anticipated to be large (change from 10% to 30%), we have very high power to detect this change (range from 0.8585 to 99.98).

We will survey 1 caregiver per newborn (n=200).

We will survey each clinician who makes a referral through the Consultagene platform at the time of their first referral (baseline). We will administer clinician followup surveys on an annual basis. Clinician qualitative interviews. About 10 clinicians will be interviewed ~12 months after implementation; all clinicians who make a referral will be invited to participate. Interviews will focus on barriers and facilitators to using the Consultagene platform, satisfaction with and suggested improvements, and perceived fidelity to the intervention.

G2. Data Analysis

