Provide a description of your plan for data analysis. State the types of comparisons you plan (e.g. comparison of means, comparison of proportions, regressions, analysis of variance). Which is the PRIMARY comparison/analysis? How will the analyses proposed relate to the primary purposes of your study?

Primary outcome: Descriptive statistics (proportion and 95% CI) will be presented for each NICU and for all NICUs at each time point. Approximately 40 babies will be recruited per year over 5 years. Cluster or NICU effect will be taken into account when calculating overall data (proportion and 95% confidence intervals). To compare changes before and after intervention (the percent of babies with a diagnosis based on genetic evaluation over the total number of babies suspected to have a genetic diagnosis), mixed-effects model will be used to take into account both time effect and clustering (NICU) effect.

Secondary outcomes: Descriptive statistics (proportion and 95% CI, mean, standard deviation, median, range) of all studied variables collected in caregiver surveys will be examined. Descriptive data will be presented for each NICU and for all NICUs at each time point.

Clinical Outcomes: We will calculate descriptive statistics on patient clinical presentations, such as HPO terms and clinical diagnoses, to characterize the clinical presentation of the patient population, as well as on institutional features of the NICU, such as care level and geographic location, to characterize features of the care setting. Additionally, we will calculate descriptive statistics on clinically relevant laboratory outcomes, such as the turnaround time and outcome (diagnostic versus non-diagnostic) of each test in the multi-omics pipeline and the combined analyses for a particular patient. We will use logistic regression analysis to calculate the odds of WGS diagnosis based on clinical characteristics.

Section H: Potential Risks/Discomforts

H1. Potential Risks/Discomforts

Describe and assess any potential risks/discomforts; (physical, psychological, social, legal, or other) and assess the likelihood and seriousness of such risks:

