Do anticipated benefits outweigh potential risks? Discuss the risk-to-benefit ratio.

The anticipated benefits outweigh potential risks. The risk-to-benefit ratio remains low.

Section J: Consent Procedures

J1. Waiver of Consent

Will any portion of this research require a waiver of consent and authorization?

No

J1a. Waiver of requirement for written documentation of Consent

Will this research require a waiver of the requirement for written documentation of informed consent?

Yes

Explain how the research involves no more than minimal risk to the participants, and the specifics demonstrating that the research does not involve procedures for which written consent is normally required outside of the research context.

Waiver of requirement for written documentation of consent is requested for Clinician surveys and interviews. Individuals typically do not sign to participate in interviews/surveys outside of the research context. Clinicians will be interviewed approximately 6-12 months after implementation of the study. Interviews will focus on barriers and facilitators to using the Consultagene platform, satisfaction with and suggested improvements to Consultagene, and perceived fidelity to the intervention. We will reach out to clinicians via email and/or phone to request their participation in an interview. Informed consent will be obtained using a verbal consent statement as approved by the Institutional Review Board. The script is included in section S. Verbal consent will be recorded on audio (will be transcribed as well) and documented as such.

Verbal consent will be audio-recorded before beginning the interviews. Some participants may feel uncomfortable or upset while discussing their experiences, but they will have the option to skip questions they do not wish to answer. Although there is a slight risk of a confidentiality breach, patient data will be stored securely on a HIPAA-compliant BCM platform. The study staff will take every possible measure to minimize these risks.

J2. Consent Procedures

Who will recruit subjects for this study?

PI
PI's staff

Describe how research population will be identified, recruitment procedures, any waiting period between informing the prospective participant and obtaining consent, steps taken to minimize the possibility of coercion or undue influence and consent procedures in detail.

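### The primary denominator is all suspected babies, but the consent-first data route gives never-referred and declining infants no way into the data

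*Protocol*

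**What the plan says.** G2 defines the primary measure as the share of babies diagnosed through genetic evaluation, taken "over the total number of babies suspected to have a genetic diagnosis", and compares it before and after the intervention with a mixed-effects model. G1 uses the same frame. It puts the usual-care yield at about 1 in 10 and expects that, once the platform runs, "30% of babies who need genetic screening will get a diagnosis". That 30% is built on full uptake: all who need screening (10/10), and the roughly 6 in 10 who need genomics, receive it, and half of the latter are diagnosed.

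The data route is set out elsewhere:

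- F1: "Data will be collected via Consultagene, surveys, and qualitative interviews".
- F2: "Providers will enter individuals' data into Consultagene after informed consent is obtained". J2 gives the same order, with consent before clinical information is submitted.
- J2 then describes acceptance of the baby by the study team. F2 adds: "Families accepted in the study will be contacted by the study team at BCM".
- J1 asks "Will any portion of this research require a waiver of consent and authorization"; the answer is No. The waiver under J1a concerns only written documentation of consent for clinicians.
- G1 gives a total of 410 subjects, specimens or charts, without itemising it.
- The exclusion criteria in F1 include, as number 11, "hemodynamically unstable newborns needing transport for higher level of care".

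**The concern.** The primary outcome is the effectiveness of a platform, and NICUs are the randomised units. A NICU that seldom refers, or whose families often decline, is one where the platform works less well. The denominator in G2 would capture this; the data route would not. A suspected, eligible infant who is never referred or whose parents refuse has no described way into any of the named data sources after crossover. Participation is voluntary, so some refusals must be expected.

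What would be measured is the yield among consented infants. That answers a narrower question about sequencing in families who take it up. It departs from the stated measure in a direction that probably, though not certainly, favours the intervention. A statistical analysis plan cannot repair this, because it cannot analyse infants whose data were never collected.

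**Working it through.** **1. Who is counted in the plan's own numbers.**
- Newborns: 40 per year × 5 years = 200 (G2). Caregivers surveyed: 200 (G1). Clinicians interviewed: about 10 (G1). 200 + 200 + 10 = 410, the stated total. The sum fits with no place left for infants known only from a chart or log.
- Babies in the power model: 9 NICUs × 4 periods × 4, 5 or 6 babies = 144, 180 or 216. Four periods come from reading the triads as three crossover steps. The range brackets the 200 recruits, so the analysed babies appear to be the enrolled ones.

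**2. The stated power.** Inputs: 9 clusters (I), 4 periods (T), 3 NICUs crossing at each step, 10% against 30%, intra-class correlation (ICC) 0.5 to 0.7, m = 4 to 6 babies per NICU and step. Two-sided alpha of 0.05 is assumed. With the Hussey-Hughes variance and total variance 0.10 × 0.90 = 0.09:

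τ² = ICC × 0.09; σ² = (1 − ICC) × 0.09 / m

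Var = Iσ²(σ² + Tτ²) / [(IU − W)σ² + (U² + ITU − TW − IV)τ²]

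Here U = 18 is the number of exposed NICU-periods. W = 3² + 6² + 9² = 126 sums the squared period totals, and V = 3 × (9 + 4 + 1) = 42 sums the squared NICU totals.

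For m = 4 and ICC 0.5, τ² = 0.045 and σ² = 0.01125:

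Var = 9 × 0.01125 × 0.19125 / (36 × 0.01125 + 90 × 0.045) = 0.01936 / 4.455 = 0.00435, so SE = 0.0659

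Power = Φ(0.20 / 0.0659 − 1.96) = 0.8585, the plan's lower figure. At m = 6 and ICC 0.7 the result is 0.9973, close to the plan's upper figure if its 99.98 is read as a percentage.

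**3. Effect of non-enrolment.** Let u be the share of suspected infants enrolled after crossover (assumed; the protocol gives none) and q the yield in those not enrolled. Enrolled infants are given the plan's 30% and control periods its 10%.

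- Yield over all suspected: 0.30u + q(1 − u)
- Effect shown from enrolled infants: 0.30 − 0.10 = 20 points
- Overstatement: (1 − u)(0.30 − q)

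| u | Yield, q = 0.10 | True effect (points) | Overstatement (points) | Power range for the true effect |
|---|---|---|---|---|
| 0.9 | 28% | 18 | 2 | 0.779 to 0.989 |
| 0.8 | 26% | 16 | 4 | 0.680 to 0.967 |
| 0.7 | 24% | 14 | 6 | 0.565 to 0.913 |
| 0.5 | 20% | 10 | 10 | 0.329 to 0.659 |

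The power column uses the model of step 2 with the smaller effect and unchanged babies per step; its ends are m = 4 with ICC 0.5 and m = 6 with ICC 0.7.

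**4. Sensitivity to q.** At u = 0.8 the overstatement is 6 points if q = 0, 4 if q = 0.10, 2 if q = 0.20 and 0 if q = 0.30. At q = 0.40 the effect is understated by 2 points.

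**The case against.** The strongest reply is that G2 already names the right denominator. No passage prescribes an analysis restricted to enrolled infants; a reader might infer a per-protocol analysis, but that follows from the data flow and is not written. Screening logs and analysis sets are often left to other documents. F2 also has the provider inform the research coordinator once a neonate needs genetics consultation, so staff can know of some infants before consent, and J1 does not address plain counts per NICU. The 410 is not itemised in the protocol. All of this stands as a limit on how firmly the point can be put. It does not supply a route for the diagnosis status of infants never referred or whose parents decline.

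Three stronger readings fail:

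- **Infants not accepted are lost.** Under J2 they have been consented and submitted before acceptance, so their records may exist. The protocol does not say whether they count.
- **Transported infants are lost to the intervention phase.** Criterion 11 makes unstable infants needing transport ineligible, and it is not limited to one phase. The protocol does not address transfer of otherwise eligible infants before consent.
- **The apparent effect could be 40 points.** This sets the 50% yield among infants who get genomics (G1) against 10% among all who need screening. The populations differ, and the gap would arise even at full uptake, so it does not measure non-enrolment.

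Nor is overstatement certain. It needs a lower yield in the infants left out than in those enrolled. It also depends on how control infants are ascertained, which the protocol does not describe. If they too need consent, both phases are restricted and the bias may shrink.

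**Conclusion.** The point holds as a contradiction between the primary measure and the data route. Followed as written, the protocol would not deliver diagnoses over all suspected babies, because never-referred and declining infants are likely to be absent after crossover. Overstatement is probable rather than shown: 2 to 10 points for assumed uptake of 90% down to 50%, if those outside the study have the plan's 10% yield. To remove the bias by yield alone, they would need 30%, three times the usual-care figure. The point does not rest on transported or non-accepted infants, and it does not claim that the plan prescribes a per-protocol analysis.

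**What to change.** Reconcile G2 with F1, F2, J1 and J2 in one of two ways.

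- **Preferred.** Keep a minimal de-identified log, in both control and intervention periods, of every infant at each NICU who meets the same eligibility criteria. Record period, referral status, enrolled or reason not, and diagnosis yes or no. Request a limited waiver for it in J1, use it as the primary denominator, and report yield among sequenced infants as secondary. Infants excluded by criterion 11 stay out in both phases. Consented but non-accepted infants who meet the criteria are counted.
- **Otherwise.** Restate the primary denominator as consented infants and limit the conclusion to them.

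The log must cover both phases, since fixing only the intervention phase would create a new imbalance. The cost is an IRB amendment, a short log that the local coordinators already planned could keep, and probably a smaller apparent yield. Non-enrolment is hard to reconstruct later, so the change should precede the first crossover.

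### Start times are randomised using matched triads of NICUs, but the primary model and the power calculation account only for time and NICU, and F1 does not make clear whether triads or NICUs within triads are the randomised unit.

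*Protocol*

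**What the plan says.** Protocol section F1 (Design) describes a stepped-wedge cluster-randomised trial in "nine under-resourced NICUs, matched into cohorts based on size (number of beds), and rural/urban status". It then says that "we will have cohort triads (three NICUs each) which will be simultaneously randomized to the time at which the intervention is implemented". This can be read in two ways: each triad moves as a block to one start time, or the three NICUs in each triad are spread across the start times.

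Section G2 (Data Analysis, primary outcome) states that for the before-and-after comparison of diagnostic yield a "mixed-effects model will be used to take into account both time effect and clustering (NICU) effect". No triad term is named.

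Section G1 (Sample Size) bases power on the NICU as the cluster: "we use different sizes of the cluster (4, 5, 6) i.e. number of babies per NICU requiring genetic screening" in each time step, correlations of 0.5, 0.6 and 0.7, and a change from 10% to 30%. It admits to having no prior data on the correlation. The triad does not appear in G1 either.

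**The concern.** An analysis should follow the allocation. The triad is part of how start times are assigned, but the stated model treats the nine NICUs as exchangeable and independent.

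- **NICUs randomised within triads.** Differences between triads are balanced by design. A model without triad leaves them in the NICU variance, so the standard error is somewhat too large and the benefit of matching is not collected.
- **Whole triads starting together.** NICUs in a triad share both characteristics and start time. A model that treats them as independent gives a standard error that is too small. Any change over time shared within a triad is then mixed up with the intervention effect, and only three units have been randomised.

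At stake are the confidence interval and p-value for the primary outcome, and the power claimed in G1.

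**Working it through.** **Inputs from the protocol:** 9 NICUs in 3 triads; 4, 5 or 6 babies per NICU per step (m); intra-class correlation (ICC) 0.5, 0.6 or 0.7; 10% to 30%.

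**Assumed, because the protocol gives no figure:** 3 start times and 4 periods, two-sided 5% test, total variance 0.1 × 0.9 = 0.09, triad share of the between-NICU variance 25%, 50% or 75%, and the between-period correlation of the triad effect (1, 0.9 or 0.8).

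**1. The plan's own power.** The Hussey-Hughes variance, with τ² = ICC × 0.09 and s² = (1 − ICC) × 0.09 / m, is

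Var = I·s²(s² + T·τ²) / [(I·U − W)s² + (U² + I·T·U − T·W − I·V)τ²].

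Here I = 9, T = 4, U = 18, W = 126 and V = 42, so the brackets are 162 − 126 = 36 and 324 + 648 − 504 − 378 = 90.

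- m = 4, ICC 0.5: τ² = 0.045, s² = 0.01125. Var = 9 × 0.01125 × 0.19125 / (36 × 0.01125 + 90 × 0.045) = 0.01936 / 4.455 = 0.004347, so SE = 0.0659. Power = Φ(0.2/0.0659 − 1.96) = 0.8585, exactly G1's lower figure with no triad term.
- m = 6, ICC 0.7: SE = 0.0422, power 0.9973. G1 gives 99.98, read as 0.9998, so the upper end is close but not exact.

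**2. Triad effect constant over time, ICC 0.5 to 0.7.** The standard error reported by the time-plus-NICU model was divided by the true one, over m = 4 to 6 and shares of 25% to 75%.

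- Within triads: ratio 1.001 to 1.012, type I error 4.7% to 5.0%. At m = 4 and ICC 0.5, adding triad lifts power from 0.8585 to 0.862, 0.8685 and 0.884 at the three shares, a gain of at most about 2.6 points. At m = 6 and ICC 0.7 there is almost no gain (0.9973 to 0.9978 at most).
- Whole triads: ratio 0.977 to 0.998, type I error 5.1% to 5.6%.

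The NICU random effect already absorbs nearly all of a constant triad difference when the ICC is this large.

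**3. Lower ICC, as a sensitivity check.** At ICC 0.1 and m = 5, for shares of 25/50/75%:

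- Within triads, the SE is 1.4/2.8/4.3% too large. Adding triad raises power from 0.772 to 0.785/0.804/0.833.
- Whole triads, the ratio is 0.974/0.950/0.928 and type I error 5.6/6.3/6.9%.

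**4. Triad effect varying by period, 50% share.** The time-plus-NICU model was fitted by REML to 1,500 simulated trials per scenario (Gaussian approximation). With whole triads starting together:

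- m = 4, ICC 0.5: ratio 0.79 and 0.68, type I error 0.13 and 0.19, at between-period correlations 0.9 and 0.8.
- m = 6, ICC 0.7: ratio 0.59 and 0.48, type I error 0.26 and 0.33.

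With NICUs randomised within triads, the same scenarios give ratios of 0.99 to 1.05 and type I error of 0.039 to 0.051.

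**5. Does a triad intercept help in case 4?** No. In closed form at correlation 0.9, the ratio for whole triads is 0.79 (m = 4, ICC 0.5) and 0.57 (m = 6, ICC 0.7), with or without the intercept. An analysis that models the triad-by-period variation is valid, but its power at correlations 0.9 and 0.8 is 0.668 and 0.538 in the first setting, and 0.771 and 0.555 in the second.

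**6. Number of possible allocations.** Whole triads: 3! = 6, so the smallest one-sided randomisation p-value is 1/6 = 0.167. Within triads: (3!)³ = 216, and 1/216 = 0.005.

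**The case against.** The strongest reply is that G2 is a short summary. It does not say that time and NICU are the only terms, and a statistical analysis plan that is not shown may add the triad. At the protocol's own correlations, with a constant triad effect, the omission moves the standard error by about 2% at most. The triad share and the between-period correlations are assumptions, and the larger constant-effect figures come from an ICC of 0.1, which G1 does not use.

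Much of this stands, and it limits the size of the point. It does not remove it. The protocol chose to state the primary model's structure and the power basis, and neither matches the allocation in F1. G1 also has no prior ICC data, so lower values cannot be excluded.

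A reader might infer that the primary error bars are materially wrong whichever way F1 is read. The protocol's figures do not support that: with randomisation within triads the stated model is valid and slightly conservative. A reader might also infer that one triad term repairs both readings. That holds only if triad effects are constant over time.

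**Conclusion.** The stated analysis and power leave out a grouping that the randomisation uses, and F1 leaves the randomised unit open. The consequence depends on which reading is meant.

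- **Within triads:** the loss is minor. The SE is up to about 1% too large and about 0 to 2.6 power points are forgone, at ICC 0.5 to 0.7 and assumed shares of 25% to 75%.
- **Whole triads, constant triad effect:** the SE is up to about 2% too small and type I error is up to about 5.6%.
- **Whole triads, shared period-to-period changes:** the model can be clearly anti-conservative, with type I error of about 0.13 to 0.33. This rests on an assumed 50% share and correlations of 0.8 to 0.9, so it shows what could happen and is not an estimate for these NICUs.

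In the first two cases the errors grow at lower ICCs. The change should be made; it is not a fatal flaw.

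**What to change.** 1. In F1, state whether whole triads, or NICUs within triads, are randomised to start time.
2. If NICUs are randomised within triads, add the matched triad (three levels) in G2 as a fixed effect alongside period, intervention status and the NICU random effect. The cost is one sentence and two more parameters with nine NICUs.
3. If whole triads start together, treat the triad as the randomised unit in G2, through triad-by-period variation in the model or inference at triad level, and restate the G1 power on that basis. The cost is a new power calculation and probably a lower figure. With only six possible allocations, randomisation-based inference at triad level cannot give a one-sided p-value below 0.167.

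No new data are needed in either case. The choice should be fixed before outcome data are seen, because adding or dropping the term later would be a post hoc decision.

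### G2 allows for NICU clustering in the primary outcome but does not extend this to the logistic regression for WGS diagnosis or to the pooled caregiver-survey confidence intervals

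*Protocol*

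**What the plan says.** The design has few clusters (Protocol F1): "The Consultagene platform will be implemented in nine under-resourced NICUs, matched into cohorts based on size (number of beds), and rural/urban status". 

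For sample size, G1 says of the NICU correlation: "We do not have prior data on intra-class correlation for NICUs, but we expect it to be large". The values used there are 0.5, 0.6 and 0.7, under the heading of the primary-outcome power calculation. G1 also plans a survey of one caregiver per newborn, 200 in all.

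Section G2 then treats three groups of analyses differently:

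- **Primary outcome.** "Cluster or NICU effect will be taken into account when calculating overall data (proportion and 95% confidence intervals"). A mixed-effects model with time and NICU effects is named for the comparison before and after implementation.
- **Secondary outcomes.** "Descriptive statistics (proportion and 95% CI, mean, standard deviation, median, range) of all studied variables collected in caregiver surveys will be examined". These are to be shown for each NICU and for all NICUs at each time point. Clustering is not mentioned.
- **Clinical outcomes.** "We will use logistic regression analysis to calculate the odds of WGS diagnosis based on clinical characteristics". Clustering is not mentioned.

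**The concern.** Infants in the WGS regression and caregivers in the surveys come from the same NICUs as the primary-outcome data. Infants enter by local provider referral (F2), and NICUs differ in size and rural or urban setting (F1), so case mix and family experience may be more alike within a NICU than between NICUs. The protocol accepts this principle for the primary outcome and then does not carry it over. Someone following G2 as written would fit a mixed-effects model in one place and a logistic regression without a NICU term in another.

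Two things are at stake. Pooled survey intervals would look more precise than they are. In the regression, a characteristic that partly marks which NICU an infant came from could appear to predict a WGS diagnosis more firmly than the data allow.

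**Working it through.** **The plan's own figure.** The protocol states no figure for these two analyses. Its only statistical figure is the primary-outcome power in G1. A standard stepped-wedge calculation (nine NICUs, three steps of three, four periods, 10% against 30%, total variance 0.1 × 0.9 = 0.09, two-sided 5% level assumed) gives 0.8585 at 4 babies per step and ICC 0.5, which matches the stated lower end. It gives 0.9973 at 6 babies and ICC 0.7, close to the stated upper end of 99.98 if that is read as a percentage. So 0.5 to 0.7 enters as the correlation of the primary outcome, and only there.

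**Pooled caregiver CIs**

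Inputs: 200 caregivers (G1; also 40 per year × 5 years, G2) and nine NICUs (F1). Equal NICU sizes are assumed, and so is the ICC.

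- Caregivers per NICU: m = 200/9 = 22.2.
- Plain 95% half-width near 50%: 1.96 × √(0.25/200) = 6.9 points.
- Design effect: 1 + (m − 1) × ICC. The true half-width is the plain one times its square root.

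| Assumed ICC | Design effect | Half-width (points) | Plain CI too narrow by |
|---|---|---|---|
| 0.01 | 1.21 | 7.6 | 9% |
| 0.05 | 2.06 | 9.9 to 10.0 | 30% |
| 0.10 | 3.12 | 12.2 | 43% |
| 0.20 | 5.24 | 15.9 | 56% |

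The last column is 1 − 1/√(design effect); for example, 1 − 1/√2.06 = 0.30.

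If time point means study year, the pooled sample is 40 caregivers, or 40/9 = 4.4 per NICU. At ICC 0.05 the design effect is 1 + 3.4 × 0.05 = 1.17, and the plain CI is 1 − 1/√1.17 = 8% too narrow (half-width 1.96 × √(0.25/40) = 15.5 instead of 15.5 × √1.17 = 16.8 points). If it means the baseline and return-of-results surveys described in F2, the table applies. A CI computed within a single NICU contains no between-NICU variation and is not affected under either reading.

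**Logistic regression for WGS diagnosis**

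Simulation of logistic regression without a NICU term: nine NICUs of 22 infants, 50% yield (the G1 expectation among infants given genomic evaluation), no true effect of the characteristic, 1,000 runs per setting, nominal 5%. The ICC and the spread of the characteristic between NICUs are assumptions.

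| Assumed outcome ICC | Characteristic unrelated to NICU | Prevalence varies by NICU |
|---|---|---|
| 0.01 | 5.5% | 5.4% |
| 0.05 | 6.5% | 7.1% |
| 0.10 | 4.2% | 9.5% |
| 0.20 | 4.9% | 13.8% |

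A 95% interval for the odds ratio fails to cover at the same rate. The second column stays near nominal; the inflation appears only in the third, and it shrinks as the spread of the characteristic between NICUs shrinks. In a separate simulation of 2,000 runs per setting, the error was 4% to 6% once the model contained a NICU effect.

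**The case against.** The strongest reply is that the omission is read from silence. G2 does not say NICU will be ignored, and logistic regression does not by itself exclude a random intercept, a GEE or robust standard errors. Such detail is often left to the statistical analysis plan, which is not shown. This stands as a limit on the claim: the text omits the provision; it does not rule it out. But G2 makes the provision explicitly in one paragraph, names a different model in a later one, and promises pooled CIs without it. Reconciling these is more than asking for detail.

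A reader might also infer stronger versions that the protocol does not support:

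- **That p-values will be wrong.** G2 names no test or p-value for either analysis. The point concerns intervals.
- **That the plan's own ICC of 0.5 to 0.7 applies here.** At those values the survey half-width would be 23.6 to 27.6 points. But that assumption belongs to the primary outcome and was made without prior data. It is not stated for survey answers or for WGS yield among sequenced infants, who meet common criteria and are evaluated remotely by one central team.
- **That error rates of 50% or more are in prospect.** Rates of that order arise for purely NICU-level factors at large ICCs. G2 assigns care level and geographic location to description and regresses on clinical characteristics.
- **That every odds ratio is affected, or that other units will select infants by them.** Characteristics balanced across NICUs keep near-nominal error, and the protocol assigns the regression no such use.

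**Conclusion.** The point holds as an inconsistency within G2 that affects secondary analyses only. If the text is followed as written, pooled survey CIs are too narrow whenever responses correlate within NICU: about 30% at an assumed ICC of 0.05 with all 200 caregivers pooled, about 8% by study year, and not at all within one NICU. Intervals for odds ratios can under-cover, with error of about 10% to 14% instead of 5% at assumed ICCs of 0.10 to 0.20, but only for characteristics that vary between NICUs.

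These sizes rest on assumed ICCs, equal NICU sizes and an assumed spread of the characteristic, none of which the protocol gives. The direction does not depend on the exact values. The primary comparison already has its mixed-effects model and is untouched. This is a minor improvement worth making because it costs little.

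**What to change.** In G2, state that the logistic regression for WGS diagnosis will include a NICU effect, for example a random intercept. With only nine NICUs, fixed NICU effects or a GEE with a small-sample correction are also defensible, and the choice can be left to the statistical analysis plan. Extend the existing sentence on the NICU effect to the pooled secondary-outcome proportions, means and 95% CIs. Per-NICU summaries need no change.

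The cost is a sentence or two and no new data, since G2 already plans results by NICU and so needs the NICU identifier. The downside is somewhat wider pooled intervals, and wider intervals for odds ratios where a characteristic differs between NICUs.
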